- c) Includes single measurements of systolic and diastolic blood pressure, pulse rate and body temperature. All measurements to be taken after the participant has rested in a supine position for at least 5 minutes.
- d) Triplicate 12-lead ECGs (within 5 minutes) will be measured after the participant has rested in a supine position for at least 10 minutes.
- e) Dipstick analysis of protein, blood, glucose, pH and leukocytes.
- f) Hepatitis B, C, HIV 1 and 2.

Table 1 Overall Schedule of Activities (cont.)

- g) Participants will have to be fasted (water consumption is permitted) for at least 10 hours prior to full panel biochemistry laboratory safety tests (with the exception of screening and follow-up where a fasting period of 4 hours is sufficient). On Day 1, no food is permitted from 2 hours prior to dosing until 4 hours after start of the infusion. On all other days of the in-house period, standard breakfast, lunch, dinner and snack will be provided up to discharge, at the times deemed convenient by the clinical site.
- h) Intensity of adverse events will be graded on a five-point scale (Grade 1, Grade 2, Grade 3, Grade 4 and Grade 5) based on the NCI CTCAE (v5), which can be found at:
https://ctep.cancer.gov/protocoldevelopment/electronic_applications/docs/CTCAE_v5_Quick_Reference_8.5x11.pdf
- i) The Sponsor may decide to terminate PK sampling earlier and/or timing of PK sampling may be modified based on emerging PK data (e.g., consecutive postdose PK samples with below the limit of quantification [BLQ] concentration).
- j) Respiratory rate to be measured after the participant has rested in a supine position for at least 5 minutes.

█ [REDACTED]

█ [REDACTED]

[REDACTED]

█ [REDACTED]

- o) Participants will be randomized to two subgroups per dose group. One subgroup will have the CSF sampling on Day 3, the other subgroup on Day 5. The safety biomarker (blood) and coagulation sample will be taken accordingly.
- p) In case of ADA positive results at follow-up visit, the participant will be asked to come back to the unit monthly for additional ADA testing until *this is no longer clinically indicated (see Section 8.7)*. At each visit a corresponding PK sample must be also taken.

Table 1 Overall Schedule of Activities (cont.)

■	[REDACTED]
■	[REDACTED]
■	[REDACTED]
■	[REDACTED]
■	[REDACTED]

Table 2 Specific Schedule of Assessments

Procedure	Day -2	Day -1	Day 1												Day 2
			Nominal Time												

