2.3 BENEFIT/RISK ASSESSMENT

No therapeutic benefit is anticipated for participants in this study as is common for Phase 1 studies involving healthy volunteers. There is no previous clinical experience with RO7126209 – this is a ‘first-in-human’ study.

The eligibility criteria, the study design, and procedures adopted are considered to be appropriate for the safe conduct of the planned study. Participants will be closely monitored for safety consistent with standard practices for first-in-human studies, and under continuous medical observation during the study (until Day 10). The investigative site will be equipped with resuscitation equipment.

This study is adaptive in nature and planned doses may be adjusted (increased, decreased, or repeated) or intermediate doses explored based on emerging safety, tolerability, and PK data. The starting dose of 0.1 mg/kg (see Section 4.3.1) is expected to be well tolerated and associated with no or only minimal effect(s).

[REDACTED]

[REDACTED]

[REDACTED]

[REDACTED]

[REDACTED]

[REDACTED]

[REDACTED]

[REDACTED]

[REDACTED]

[REDACTED]

Overall, the level of risk for healthy participants is considered acceptable as it is mitigated by careful monitoring, sentinel cohorts at every new ascending dose level, careful dose escalation, and study stopping criteria.

More detailed information about the known and expected benefits in the context of potential risks and reasonably expected AEs of RO7126209 is provided in the RO7126209 IB.

3. **OBJECTIVES AND ENDPOINTS**

The objectives and corresponding endpoints are provided in [Table 3](#).

Table 3 Objectives and Endpoints

Objectives	Endpoints
Primary	

 • To evaluate the safety and tolerability of single ascending intravenous doses of RO7126209 in healthy participants 	
 • Incidence, severity, and causal relationship of AEs. • Incidence of abnormal laboratory findings. • Incidence of abnormal vital signs and electrocardiogram (ECG) parameters
Secondary	

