4.1.1 Length of the Study

The total duration of the study for each participant will be approximately 16 weeks divided as follows:

- Screening: Up to 8 weeks
- In clinic period: Days -2 to 10
- Final follow-up: Day 57 ± 4

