Appendix 4 Clinical Laboratory Tests

The tests detailed in [Table 1](#) will be performed by the central or local laboratory. The results will be entered into the eCRF or loaded electronically.

Protocol-specific requirements for inclusion or exclusion of participants are detailed in Sections [5.1](#) and [5.2](#), respectively, of the protocol.

Additional tests may be performed at any time during the study as determined necessary by the Investigator or required by local regulations.

Table 1 Protocol-Required Safety Laboratory Assessments

Laboratory Assessments	Parameters
Full Hematology	
 [REDACTED]
[REDACTED]	
 [REDACTED]
Full Clinical Blood Chemistry	
 ALT, AST, ALP, GGT, total, direct and unconjugated bilirubin, total protein, haptoglobin, albumin, sodium, chloride, potassium, phosphate, calcium, creatinine, urea, fasting glucose, total cholesterol, triglycerides, CPK, LDH, [REDACTED]
[REDACTED]	
 [REDACTED]
Coagulation	
 Prothrombin time (INR) and activated thromboplastin time (APTT).
Viral Serology	
 HIV (specific tests HIV1 antibody, HIV-1/2 antibody, HIV-2 antibody), hepatitis B surface antigen (HBsAg), hepatitis C virus (HCV) antibody.
Safety Biomarkers	
 [REDACTED] [REDACTED]

Laboratory Assessments	Parameters
Infusion-related reaction blood sample	
 • [REDACTED]
Thyroid Hormones	
 • Thyroid stimulating hormone (TSH) at screening only
Anti-Drug Antibodies	
 • Anti-RO7126209 antibodies in plasma will be determined using a validated ELISA method
Urinalysis	
 • Dipstick: pH, glucose, blood and protein. If there is a clinically significant positive result (may be confirmed by a positive repeated sample), urine will be sent to the laboratory for microscopy and culture. If there is an explanation for the positive dipstick results, it should be recorded and there is no need to perform microscopy and culture. • Microscopic examination (sediment, RBCs, WBCs, casts, crystals, epithelial cells, bacteria), if blood or protein is abnormal.
Alcohol	
 • Urine

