Drugs of abuse	
 • Urine tests for (at minimum): amphetamines incl. MDMA, cocaine, opiates, cannabinoids, methadone and benzodiazepines.

The results of each test will be provided electronically or captured into the CRF. Investigators must document their review of each laboratory safety report.

Additional Statistical Considerations for Clinical Laboratory Data

- Standard Reference Ranges and Transformation of Data

Potential analysis considerations for analysing Laboratory data includes the use of Standard Reference Ranges and potential transformation of data for specific lab tests.

In this scenario, Roche standard reference ranges, rather than the reference ranges of the Investigator, can be used for specific parameters. For these parameters, the measured laboratory test result will be assessed directly using the Roche standard reference range. Certain laboratory parameters will be transformed to Roche's standard reference ranges.

A transformation will be performed on certain laboratory tests that lack sufficiently common procedures and have a wide range of Investigator ranges, e.g., enzyme tests that include AST, ALT, and alkaline phosphatase and total bilirubin. Since the standard reference ranges for these parameters have a lower limit of zero, only the upper limits of the ranges will be used in transforming the data.

- Definition of Laboratory Abnormalities

For all laboratory parameters included in this analysis, there exists a Roche predefined standard reference range. Laboratory values falling outside this standard reference range will be labeled “H” for high or “L” for low in participant listings of laboratory data.

In addition to the standard reference range, a marked reference range has been predefined by Roche for these laboratory parameters. The marked reference range is broader than the standard reference range. Values falling outside the marked reference range that also represent a defined change from baseline will be considered marked laboratory abnormalities (i.e., potentially clinically relevant). If a baseline value is not available for a participant, the midpoint of the standard reference range will be used as the participant’s baseline value for the purposes of determining marked laboratory abnormalities. Marked laboratory abnormalities will be labeled in the participant listings as “HH” for very high or “LL” for very low.

Appendix 5

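### Glucose and triglycerides at Day 57 may be measured after a shorter fast than at Day -2 and every other post-dose panel, so flags and changes from baseline at that visit are not strictly comparable

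*Combined protocol and SAP*

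**What the plan says.** Table 1 footnote g sets the general rule, a fast "for at least 10 hours prior to full panel biochemistry laboratory safety tests". It then relaxes that rule for two visits: "with the exception of screening and follow-up where a fasting period of 4 hours is sufficient". Table 2 footnote a and Section 5.3.1 give the same rule. Section 4.1.1 identifies the follow-up visit: "Final follow-up: Day 57 ± 4". The overview in Section 1.2 labels Days 15 to 43 as ambulatory visits, separate from follow-up, so the exception does not reach them.

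The full chemistry panel in Appendix 4 contains "creatinine, urea, fasting glucose, total cholesterol, triglycerides, CPK, LDH". The primary endpoints in Section 3, Table 3 include "Incidence of abnormal laboratory findings".

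Appendix 4 also sets the flags. For the basic flag: "Laboratory values falling outside this standard reference range will be labeled “H” for high or “L” for low in participant listings". For the stronger flag: "Values falling outside the marked reference range that also represent a defined change from baseline will be considered marked laboratory abnormalities". It describes one standard range per parameter and no separate range by fasting state. Table 10 in Section 9.3.2 presents laboratory values as individual listings with abnormal results flagged.

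**The concern.** The protocol treats fasting as part of the measurement: it names the analyte fasting glucose and sets a 10-hour minimum. It then relaxes that condition at one post-dose visit only. A Day 57 glucose or triglyceride value may thus be read against the same range, and against the same participant's Day -2 value, although the interval since the last meal could be much shorter.

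What is at stake is how single results are read. Day 57 is the last scheduled panel, and the preceding one is on Day 29, four weeks earlier. A new flag at Day 57 could be taken for a late or unresolved drug effect when it follows a meal. The published text contains no instruction to record hours fasted, so a reader of the listing could not separate the two explanations.

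**Working it through.** **1. Fasting rule at each scheduled chemistry panel** (ticks in Table 1, matched to footnote g)

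| Panel | Setting | Minimum fast |
|---|---|---|
| Screening | before admission | 4 h |
| Day -2 | in clinic, last panel before dosing | 10 h |
| Day 2 | in clinic | 10 h |
| Day 8 | in clinic | 10 h |
| Day 15 | ambulatory | 10 h |
| Day 29 | ambulatory | 10 h |
| Day 57 | follow-up | 4 h |

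Four of the five post-dose panels need 10 hours; one of five (Day 57) needs 4. The gap between the last two panels is 57 − 29 = 28 days. Days 15 and 29 are outpatient visits under the 10-hour rule, so attending from home does not explain the exception at Day 57.

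**2. Participants covered by the rule.** Section 9.1 gives at least 4 active + 2 placebo at each of dose levels 1 and 2, and at least 6 active + 2 placebo from dose level 3. With five planned levels:

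2 × (4 + 2) + 3 × (6 + 2) = 12 + 24 = 36,

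which reproduces the stated 36. Of these, 2 × 4 + 3 × 6 = 26 are active and 5 × 2 = 10 are placebo. All 36 are permitted the shorter fast at Day 57. That is a ceiling on how many could be affected, not an estimate of how many would be.

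**3. Size of effect: not in the documents.** To show how flag counts would respond, assume that values after a 10-hour fast are normally distributed, that the upper limit is their 97.5th percentile, and that the shorter fast moves the Day 57 mean upward by s standard deviations, with s from 0 to 1. The shift and its direction are assumptions for illustration only. Per analyte:

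P(high flag) = 1 − Φ(1.96 − s)

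| Assumed shift s | P(high flag) | Expected flags, 26 active | Expected flags, 10 placebo |
|---|---|---|---|
| 0 (same fasting rule) | 2.5% | 0.65 | 0.25 |
| 0.25 SD | 4.4% | 1.13 | 0.44 |
| 0.5 SD | 7.2% | 1.88 | 0.72 |
| 1 SD | 16.9% | 4.38 | 1.69 |

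The expected counts are 26 × P and 10 × P, using unrounded P. The probability is the same in both arms, so the expected active-minus-placebo difference in rate is 0 in every row. Only the absolute number of flags and the change from Day -2 can move.

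**The case against.** The case against acting is substantial, and most of it stands.

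- The exception is deliberate. It is worded consistently in three places and nothing contradicts it.
- Four hours is a minimum. Participants may arrive after a longer fast, so a shift is possible but not shown.
- The documents give no size or direction of effect for either analyte.
- The stronger flag needs a value outside a broader marked range as well as a defined change from baseline. Neither the range nor the change is given, so whether a shorter fast could trigger that flag cannot be determined.
- Day -2 is not named as the laboratory baseline. It is the natural reading, as the last chemistry panel before dosing.
- Section 8.2.5 requires unexplained, clinically significant results to be repeated and followed up, and allows extra samples when a result is out of range. Section 8.10.5 continues adverse event follow-up after the last visit.
- Dose-limiting events count only within 8 days of dosing (Section 9.3.4), so Day 57 results cannot enter the dose-escalation model.
- Placebo participants follow the same rule, so the arms remain comparable in expectation.

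A reader might infer that final-visit glucose and triglycerides are biased towards abnormal, that false marked abnormalities will follow, or that a fifth of post-dose results in all 36 participants are distorted. The documents support none of these, for the reasons just listed.

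The objection does not remove the mismatch itself. Equal treatment of the arms protects a group contrast, but Table 10 plans individual flagged listings for laboratory data and mentions tabular summaries only for vital signs and ECG. A flag read one participant at a time has no such protection. With about 2 placebo participants per dose level, a within-cohort comparison gives little help. The repeat-test rule covers results judged clinically significant and unexplained; for other out-of-range values a repeat is discretionary.

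**Conclusion.** The point holds as a minor inconsistency in measurement conditions. One of five scheduled post-dose panels, the last, may be drawn after 4 hours without food, whereas Day -2 and the other four need at least 10. For fasting glucose and triglycerides, the Day 57 value and its change from baseline are therefore not necessarily comparable with the rest of the series, and a flag there may reflect a recent meal.

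The size of any effect is unknown. Under the illustrative range of 0 to 1 SD upward, expected high flags per analyte among 26 active participants run from 0.65 to 4.38, with the same rate on placebo. No dose decision or expected between-arm comparison is affected.

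The conclusion rests on two readings: that follow-up in the footnotes means the Day 57 visit, which Sections 1.2 and 4.1.1 support, and that Day -2 serves as the laboratory baseline, which is reasonable but not stated.

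**What to change.** Remove follow-up from the 4-hour exception in Table 1 footnote g, Table 2 footnote a and Section 5.3.1, so that Day 57 has the same 10-hour minimum as Days -2, 2, 8, 15 and 29. The screening exception can stay, because the Day -2 panel provides a pre-dose value under the 10-hour rule.

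The cost is a wording change in three places, with no new sample or visit. Participants would have to attend Day 57 fasted overnight, as they already do on Days 15 and 29.

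If the sponsor prefers to keep the shorter fast, the fallback is to record hours fasted at Day 57 and state how glucose and triglyceride flags and changes from baseline at that visit will be interpreted. That leaves the mismatch in place but makes it visible in the listing.

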2. INTRODUCTION

2.1 STUDY RATIONALE

RO7126209 is a bispecific (2+1) monoclonal antibody (mAb) construct that combines, by recombinant fusion the anti-A β antibody gantenerumab with a Brain Shuttle module that [REDACTED] RO7126209 is being developed for the treatment of Alzheimer's Disease (AD). This is the first study in which RO7126209 will be administered to humans. A randomized, investigator and subject blind, adaptive, placebo-controlled, parallel design was chosen to assess the safety, tolerability, immunogenicity and pharmacokinetics (PK) following single ascending doses of RO7126209 administered intravenously to healthy participants.

The rationale for the study design is provided in Section [4.2](#).

2.2 BACKGROUND

2.2.1 Background on Disease

The World Health Organization estimates that around 50 million people worldwide are living with dementia and that 10 million new cases are diagnosed every year. The total number of people with dementia is estimated to reach 82 million in 2030 and will almost triple by 2050 to 152 million. AD is the most common form of dementia, accounting for 60%-70% of cases ([World Health Organization 2017](#)). The prevalence of AD increases with age, with a global prevalence of 5%-8% in people aged 60 years or over.

AD is clinically characterized by a progressive impairment in cognitive and executive abilities, which results in decreased function and gradual loss of independence ([Mesterton et al. 2010](#)). There is great inter-individual variability in AD progression with survival dependent on many factors, including age at onset. In general, the clinical picture evolves from “predementia” or “prodromal AD” to mild, moderate, and then severe AD. At the early stage of AD, a slight impairment of memory, language, and visuospatial function can be observed. As AD advances, patients become progressively impaired not only in terms of cognition but also in activities of daily living and the burden on caregivers significantly increases. The median survival time following a diagnosis of AD depends on the patient's age at diagnosis and ranges from 8.3 years for persons diagnosed with AD at 65 years old to 3.4 years for those 90 years old ([Brookmeyer et al. 2002](#)). On average, individuals live 6 years after diagnosis ([Helzner et al. 2008](#)).

Pathologically, AD is characterized by the presence of cerebral A β plaques, neurofibrillary tangles, and a loss of neurons. A β is a peptide derived from proteolytic processing of the amyloid precursor protein, APP. This peptide exists in two major forms: A β ₁₋₄₀ and A β ₁₋₄₂ ([Citron et al. 2004](#)). Although the etiology of AD is not completely understood, current research suggests that A β processing and deposition play a critical role in the cascade of biological events involved in the pathogenesis of the disease. Consequently, therapies targeting this process have the potential to significantly alter the progression of the disease.

Because of its increasing prevalence, long duration, and high cost of care, AD is expected to continue to represent a major public health problem for decades to come.

2.2.2 Background on RO7126209

[REDACTED]

[REDACTED]

[REDACTED]

[REDACTED]

[REDACTED]

[REDACTED]

[REDACTED]

[REDACTED]

[REDACTED]

[REDACTED]

[REDACTED]

[REDACTED]

[REDACTED]

[REDACTED]

[REDACTED]

[Redacted]

[Redacted]

[Redacted]

[Redacted]

[Redacted]

[Redacted]

[Redacted]

[Redacted]

[Redacted]

[Redacted]

[Redacted]

[REDACTED]

[REDACTED]

[REDACTED]

[REDACTED]

[REDACTED]

[REDACTED]

[REDACTED]

[REDACTED]

A detailed description of the chemistry, pharmacology, and safety of RO7126209 is provided in the RO7126209 Investigator Brochure (IB).

2.3 BENEFIT/RISK ASSESSMENT

No therapeutic benefit is anticipated for participants in this study as is common for Phase 1 studies involving healthy volunteers. There is no previous clinical experience with RO7126209 – this is a ‘first-in-human’ study.

The eligibility criteria, the study design, and procedures adopted are considered to be appropriate for the safe conduct of the planned study. Participants will be closely monitored for safety consistent with standard practices for first-in-human studies, and under continuous medical observation during the study (until Day 10). The investigative site will be equipped with resuscitation equipment.

This study is adaptive in nature and planned doses may be adjusted (increased, decreased, or repeated) or intermediate doses explored based on emerging safety, tolerability, and PK data. The starting dose of 0.1 mg/kg (see Section 4.3.1) is expected to be well tolerated and associated with no or only minimal effect(s).

[REDACTED]

[REDACTED]

[REDACTED]

[REDACTED]

[REDACTED]

[REDACTED]

[REDACTED]

[REDACTED]

[REDACTED]

[REDACTED]

Overall, the level of risk for healthy participants is considered acceptable as it is mitigated by careful monitoring, sentinel cohorts at every new ascending dose level, careful dose escalation, and study stopping criteria.

More detailed information about the known and expected benefits in the context of potential risks and reasonably expected AEs of RO7126209 is provided in the RO7126209 IB.

3. **OBJECTIVES AND ENDPOINTS**

The objectives and corresponding endpoints are provided in [Table 3](#).

Table 3 Objectives and Endpoints

Objectives	Endpoints
Primary	

 • To evaluate the safety and tolerability of single ascending intravenous doses of RO7126209 in healthy participants 	
 • Incidence, severity, and causal relationship of AEs. • Incidence of abnormal laboratory findings. • Incidence of abnormal vital signs and electrocardiogram (ECG) parameters
Secondary	

 • To investigate the single intravenous dose pharmacokinetics (PK) of RO7126209 in plasma of healthy participants • To investigate the CSF penetration after a single dose of RO7126209 in healthy participants • To evaluate the immunogenicity of a single dose of RO7126209 in healthy participants 	
 • Plasma PK parameters of RO7126209 • CSF concentration of RO7126209 • Incidence of anti-RO7126209 antibodies (ADAs)
Exploratory	

 • To explore PK/safety relationships of RO7126209 in healthy participants 	
 • Relationship between plasma exposure of RO7126209 and safety measurements

4. STUDY DESIGN

4.1 OVERALL DESIGN

An overview of the study design is provided in Section 1.2.

Study BP41192 is a randomized, adaptive, placebo-controlled parallel group study to investigate the safety, tolerability, immunogenicity and pharmacokinetics of single ascending intravenous doses of RO7126209 in healthy participants.

This study uses a parallel group design, with participants recruited in 5 planned sequential cohorts. Participants will receive a single IV dose of either RO7126209 or placebo. Thirty-six participants are expected to be enrolled in this study. [REDACTED], with the maximum number of participants not exceeding 60. A minimum of 4 active treatment and 2 placebo participants will be included in the first two dose levels. Starting at dose level 3, and in all subsequent cohorts, a minimum of 6 active treatment and 2 placebo participants will be included. Based upon the review of emerging data there will be the option to adjust the number of participants on active treatment or placebo per dose level. If a dose level is repeated or if a lower dose is investigated, the added group will consist of at least 2 participants on active and 1 on placebo.

In accordance with standard practice for first-in-human studies, RO7126209 doses will be administered in ascending order, starting with a dose of 0.1 mg/kg that is anticipated to be well tolerated (Section 4.3.1). Subsequent doses will be selected in an adaptive manner during study conduct based on emerging safety, tolerability and PK data. A Bayesian adaptive design using the continual reassessment method (CRM) for predicting (see Section 9.3.4 and Appendix 6) the anticipated maximum dose-limiting event (DLE) rate to guide dose effect relationship will also be applied for dose escalation.

Intermediate dose escalation steps other than those anticipated (Section 1.2) may be used, doses may be repeated, or adjusted based on safety, tolerability and PK data at each dose level, as well as on model-based prediction of the anticipated maximum DLE rate.

In each dose group, sentinel dosing will be employed to allow for an evaluation of safety data by the Investigator up to 48 hours following intravenous administration of RO7126209 or placebo before subsequent participants are dosed. [REDACTED]

There will be at least 2 weeks between each dose level in order to permit adequate time for collation and review of emerging data before the next dose is administered.

The participants, investigators, and site personnel (except site personnel responsible for study drug accountability, reconciliation, record maintenance and drug preparation) will be blinded to treatment assignments.

Participants in the sentinel group will receive a single IV infusion of study medication (RO7126209 or matching placebo [REDACTED])

